## Concomitant Interventions

### Allowed Interventions

*Medical therapy with steroids, antithyroid drugs or both will be ongoing peri-procedure with an increase in the ongoing anti-thyroid regimen the day of RFA and the day after the procedure after which pre-procedure doses will be resumed until thyroid levels are collected at the end of week 1 post-procedure. On a precautionary measure in the event of excess release of active T3 / T4 due to RFA, patients will be administered Lugols iodine solution (5 drops x 3 per day) starting after the procedure and continuing for the first 3 days post-RFA. Beta-blockers will be employed/increased starting 1 day before procedure and then adjusted in a manner analog with anti-thyroid regimen. These adjustments will be made in collaboration with cardiology, according to the cardiovascular status of the patient. If some of these changes are not clinically acceptable then bile-acid sequestrants will be used for their anti-thyroid effect, starting 2 days before procedure and continuing for 3 days after the procedure. If despite these interventions thyrotoxicosis will deteriorate post RFA both plasmapheresis and thyroidectomy will be discussed with the patient and pursued based on the clinical situation.*

*Of note – amiodarone can be continued during the study, at the discretion of the cardiologist consultant.*

### Required Interventions

*Beta-blockers (if agreed by cardiology) and either steroid therapy, methimazole therapy or both will be required during the study.*

## Prohibited Interventions

*There are no prohibited medications or interventions during this trial*

## Adherence Assessment

*Adherence is defined as having had at least 80% of the intended volume of thyroid parenchyma ablated and taking at least 80% of the intended medical therapy tablets by the end of week 1 post RFA. Medication adherence will be tested through pill counts.*

**Resources:** We have the commitment of the Division of Endocrinology and Department of Radiology of Mayo Clinic Rochester that they will support this study. These 2 areas have worked collaboratively in a similar project that has led to the adoption of our current RFA protocol for benign thyroid nodules. We have enlisted the collaboration of a company manufacturing RFA devices, StarMed, with some of the single use RFA instrumentation and partial financial support. Mayo Clinic is also providing support for the project through a Career Development Grant awarded to [name] that will be utilized for covering cost of laboratory tests, partial financial support for travel expenses for the patients and PI and study coordinator dedicated time to the project.

## Subject Information

Target accrual is 5 patients. To achieve this number of subjects, we will access medical records for about 100 patients.

Subject population: Adults ( $\geq 18$  years of age) with AIT who undergo treatment at Mayo Clinic, Rochester and those referred to thyroid clinic for evaluation.

### Inclusion Criteria:

We will enroll patients with AIT that meet all criteria 1 through 4 and then either criteria A or B as follows:

1. Are adults,
2. Have overt thyrotoxicosis (within 2 weeks prior to enrollment) with elevated Free and/or Total T4 and/or T3
3. Are receiving medical therapy for AIT
4. Are able to understand the study procedures and to comply with them for the entire length of the study

and:

- A. have not normalized their thyroid levels after one month of standard therapy **or**
- B. have persistent and clinically significant thyrotoxicosis (less than 25% decrease in T4 value or patients requiring hospitalization with CHF, tachyarrhythmias, hemodynamic instability or similar comorbidities) after 2 weeks of standard therapy where additional medical therapy is deemed unlikely to be beneficial or with high risk of side-effects (e.g. hepatotoxicity of antithyroid medications, agranulocytosis of potassium perchlorate or ATD or fluid retention associated with steroids).

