**Background:**

**Background on Condition, Disease, or Other Primary Study Focus**

Amiodarone induced thyrotoxicosis (AIT) is an entity developing in about 2-8 % of patients treated with amiodarone. It is considered to have a dual pathophysiology with increased thyroid hormone production in AIT type 1, and leakage of preformed thyroid hormone in a thyroiditis fashion in AIT type 2. The two types are in reality combined in many patients and combination therapy is required in such patients, which delays the therapeutic response. Furthermore even if combination therapy is used in some cases the response to therapy is suboptimal and the patients have complications related to hyperthyroidism and side-effects from the medications used. We have shown an increase in frequency of hospitalizations, CHF, weight loss and arrhythmia in this group. Some patients require thyroidectomy for adequate control of their thyrotoxicosis , a procedure not without risks in this population with cardiac comorbidities.

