## Study Design and Procedure

### STUDY DESIGN

This will be an open-label clinical trial that will target AIT patients that fail to respond to medical therapy. We will treat them with RFA therapy and then assess the clinical and biochemical response (primary objective) in the coming 4 weeks and continue to monitor the clinical response for a minimum of 3 months or until the resolution of the AIT episode, whichever occurs later. We expect that an individual will be thus in the trial for a total of 4-6 months. The safety of the RFA procedure will be assessed as well (secondary objective) in the first month after the procedure. We plan to enroll 5 patients to undergo the procedure and use a historical control group for comparison of clinical and biochemical outcomes. The study will take place at Mayo Clinic in Rochester, MN and will recruit both from our out-patient as well as the in-patient population with AIT. We expect that we would be able to identify 10-15 cases/year that would qualify for this trial and given the potential acceptance to enrollment we expect that it would take 12-18 months for the trial completion.

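### Inclusion criterion A admits patients who are already improving on drugs, although the trial is described as targeting non-responders, so drug-driven recovery could not be told apart from RFA response

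*Combined protocol and SAP*

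**What the plan says.** The STUDY DESIGN section calls this an "open-label clinical trial that will target AIT patients that fail to respond to medical therapy". The same section places the primary objective, clinical and biochemical response, in the 4 weeks after RFA. It plans 5 treated patients with a historical control group for comparison.

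Under Inclusion Criteria, patients must "meet all criteria 1 through 4 and then either criteria A or B":

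- **Criterion 2** sets the biochemical floor: "Have overt thyrotoxicosis (within 2 weeks prior to enrollment) with elevated Free and/or Total T4 and/or T3". This concerns the level, not its direction.
- **Criterion A** admits patients who "have not normalized their thyroid levels after one month of standard therapy".
- **Criterion B** requires persistent, clinically significant thyrotoxicosis, specified as "less than 25% decrease in T4 value or patients requiring hospitalization with CHF, tachyarrhythmias, hemodynamic instability or similar comorbidities". This is assessed "after 2 weeks of standard therapy where additional medical therapy is deemed unlikely to be beneficial or with high risk of side-effects".

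No item under Exclusion Criteria removes a patient whose levels are falling.

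Required Interventions makes steroid, methimazole or both mandatory during the study. Allowed Interventions raises the anti-thyroid regimen on the day of RFA and the next day, then returns to pre-procedure doses until the week 1 levels are collected. Prohibited Interventions lists nothing. The Data Analysis Plan gives medians, interquartile ranges and proportions only.

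**The concern.** Failing to respond and not yet being normal are different conditions. A patient whose hormone levels have fallen steeply over a month of drugs, but are still above normal, has responded incompletely and meets A. The Background recognises that such patients exist: in mixed disease "combination therapy is required in such patients, which delays the therapeutic response". A does not separate the slow responder from the non-responder.

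The distinction matters because drug treatment continues through the window in which RFA response is read. The documents define no response, require no run-in or pre-RFA slope, and give no rule for separating the drug's contribution from the procedure's. If an entrant was already on a falling course, normal levels at week 4 do not show which treatment produced them.

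The first three cases are also used, under PROCEDURE, to test the assumed linear link between thyroid volume and hormone level and to decide the approach for later patients. A drug-driven fall in one of those three would affect that decision as well as the final summary.

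**Working it through.** **1. Text side by side.**

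| Route | Limit on the fall already achieved | Judgement that more drug is unlikely to help or is high risk |
|---|---|---|
| STUDY DESIGN (stated target) | Implied by failure to respond | Not stated |
| Criterion A | None | None |
| Criterion B, T4 limb | "less than 25% decrease in T4 value" | Required |
| Criterion B, hospitalisation limb | None | Required |

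Only one of the three routes into the trial carries a numerical non-response test, and any one of them is enough.

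**2. The plan's own figure.** There is no sample size or power to reproduce; the Data Analysis Plan says none was calculated. The related arithmetic is the FT4 example under PROCEDURE: from 2.4 to 1.6 ng/dL, about 33%. Check: 1 − 1.6/2.4 = 0.333. It reproduces.

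**3. Drug-only course for an entrant at 2.4.** Inputs from the plan are FT4 2.4, target 1.6 and a 4-week window. These two FT4 values are the plan's illustration for choosing ablation volume, not an entry value or a response definition. The assumption, which the documents do not supply, is a constant proportional fall d per 2 weeks, before and after entry, with no RFA effect.

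- FT4 four weeks before entry = 2.4 / (1 − d)²
- FT4 four weeks after entry = 2.4 × (1 − d)²

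Break-even: (1 − d)² = 1.6/2.4, so d = 1 − √0.6667 = 0.184, or 18.4% per 2 weeks.

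| d per 2 weeks | FT4 4 weeks before entry | FT4 at entry | FT4 at week 4 | At or below 1.6? |
|---|---|---|---|---|
| 10% | 2.96 | 2.4 | 1.94 | No |
| 15% | 3.32 | 2.4 | 1.73 | No |
| 18.4% | 3.60 | 2.4 | 1.60 | Yes (break-even) |
| 25% | 4.27 | 2.4 | 1.35 | Yes |

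All four patients satisfy A. In the last row the patient had already fallen by 1 − 0.75² = 44% when enrolled.

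**4. Weight in the result.** One such patient is 1/5 = 20% of the series. The documents give no probability of normalising on drugs alone. If it were 0.1, 0.2 or 0.3 for each patient, independently (assumption), the chance of at least one among 5 is 1 − 0.9⁵ = 41%, 1 − 0.8⁵ = 67% or 1 − 0.7⁵ = 83%.

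**The case against.** **A and B are the working definition of failure.** The STUDY DESIGN sentence is a summary, and the criteria can be read as spelling it out. The Background presents delayed response as part of the clinical problem, and the Rationale argues for RFA because it acts quickly in very sick patients. A slow responder who is still overtly thyrotoxic fits that reasoning. This has force, and it is why describing the population as not yet normalised is an acceptable remedy. It also means the documents do not establish that improving patients fall outside the intended population. What remains is that the stated target and A describe different groups, and the conclusion depends on which is meant.

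**There is a historical control.** There is, so it would be wrong to say that a flat pre-RFA course is the trial's only safeguard. A control group chosen by the same criteria and followed from the same time point could show how often drugs alone succeed. The documents do not describe its selection or time origin, and the Data Analysis Plan specifies no comparison, so as written it does not resolve the question.

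**It is a 5-patient descriptive pilot.** True, and no test is being invalidated. However, the stated hypothesis is still normalisation with resolution of thyrotoxicosis, and a descriptive proportion still needs an interpretable population.

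**Stronger readings the documents do not support.**

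- A reader might infer that drug recovery *will* be counted as RFA response. How many of the 5 would enter through A while improving is unknown, no responder is defined, and declines of 10% or 15% per 2 weeks do not reach 1.6.
- A reader might infer that B is a sound non-response test that could simply be copied into A. B's hospitalisation limb sets no limit on the fall. A limit of under 25% applied over 2 weeks would also fail in the model above: a 20% fall per 2 weeks would pass it and give 2.4 × 0.8² = 1.54, below 1.6.

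**Conclusion.** The mismatch is established by the text: the stated target is failure to respond, while A, and the hospitalisation limb of B, admit patients however far their levels have already fallen. With drug treatment required through the 4-week window and no usable comparator specified, recovery due to drugs in such an entrant can be counted as RFA response and could not be distinguished from it.

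The size is conditional. With entry at 2.4, a target of 1.6 and constant proportional decline, the threshold is a fall of 18.4% per 2 weeks: faster drug-driven declines reach target without RFA, slower ones do not. Each such patient is 1 of 5. The documents give no drug-only course, so the expected number cannot be stated. This should be settled before the results are interpreted as efficacy in non-responders.

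**What to change.** Reconcile STUDY DESIGN with Inclusion Criteria in one of two ways:

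1. The sponsor defines the non-response that A is meant to capture, naming the hormone and the interval over which change is measured. The threshold is a clinical decision for the sponsor; none is proposed here.
2. The population is described as not yet normalised on medical therapy, and no efficacy conclusion is drawn for non-responders.

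In either case:

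- record at least two dated on-treatment hormone values before RFA for every entrant, from routine results;
- present each patient's post-RFA course against that pre-RFA trend;
- report entrants by route (A or B).

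The cost is slightly more data abstraction and, under option 2, a narrower conclusion. Option 1 may slow accrual. The protocol expects 10–15 qualifying cases a year, but under the present criteria, and already allows 12–18 months for 5 patients given expected acceptance. The loss from tighter eligibility cannot be quantified from the documents.

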## Exclusion Criteria:

All candidates meeting any of the following exclusion criteria at baseline will be excluded from study participation:

1. Pregnancy
2. Patients with prior neck surgery or neck radiation
3. Patients with neck anatomy that precludes easy access by RFA to the entirety of thyroid parenchyma
4. Patients on anticoagulation therapy
5. Patients with comorbidities deemed too high of a risk for general anesthesia
6. Treatment with another investigational drug or intervention (within 6 weeks of planned RFA).
7. Current drug or alcohol use or dependence that, in the opinion of the site investigator, would interfere with adherence to study requirements.
8. Inability or unwillingness of individual or legal guardian/representative to give written informed consent.

Note: Pregnant women will not be allowed to enroll on this study. Please tell your study doctor if you are pregnant or think you might be pregnant.

There is a risk of claustrophobia (fear of closed space) while the patient is under the clear plastic dome during the indirect calorimetry (REE). Fresh air comes through the dome. If the patient is unable to tolerate the measurement, it will be discontinued.

If you are a female, you must have a negative pregnancy test in order to participate in this study unless you cannot become pregnant.

You are advised not to get pregnant owing to your current health condition (hyperthyroidism); however, from this study perspective there are no restrictions to pursue pregnancy post RFA procedure.

## Research Activity

Check all that apply and complete the appropriate sections as instructed.

1.  **Drug & Device:** Drugs for which an investigational new drug application is not required. Device for which (i) an investigational device exemption application is not required; or the medical device is cleared/approved for marketing and being used in accordance with its cleared/approved labeling. (Specify in the study design and procedure section)
2.  **Blood:** Collection of blood samples by finger stick, heel stick, ear stick, or venipuncture.
3.  **Biological specimens other than blood:** Prospective collection of human biological specimens by noninvasive means that may include: urine, sweat, saliva, buccal scraping, oral/anal/vaginal swab, sputum, hair and nail clippings, etc.
4.  **Tests & Procedures:** Collection of data through noninvasive tests and procedures routinely employed in clinical practice that may include: MRI, surface EEG, echo, ultrasound, moderate exercise, muscular

strength & flexibility testing, biometrics, cognition testing, eye exam, etc. (Specify in the study design and procedure section)

5.  **Data** (medical record, images, or specimens): Research involving use of existing and/or prospectively collected data.
6.  **Digital Record:** Collection of electronic data from voice, video, digital, or image recording. (Specify in the Methods section)
7.  **Survey, Interview, Focus Group:** Research on individual or group characteristics or behavior, survey, interview, oral history, focus group, program evaluation, etc. (Specify in the Methods section)

NIH has issued a *Certificate of Confidentiality* (COC). *When checked, provide the institution and investigator named on the COC and explain why one was requested.* \_\_\_\_\_

#### **Biospecimens – Categories 2 and 3**

(2) Collection of blood samples. When multiple groups are involved copy and paste the appropriate section below for example repeat section b when drawing blood from children and adults with cancer.

- a. **From healthy, non-pregnant, adult subjects who weigh at least 110 pounds.** For a minimal risk application, the amount of blood drawn from these subjects may not exceed 550ml in an 8 week period and collection may not occur more frequently than 2 times per week.

Blood samples will be obtained; Volume10 cc per clinical visit and 10 cc for research (3 time points)

- b. **From other adults and children considering age, weight, and health of subject.** For a minimal risk application, the amount of blood drawn from these subjects may not exceed the lesser of 50 ml or 3 ml per kg in an 8 week period, and collection may not occur more frequently than 2 times per week.

No blood samples will be obtained.

(3) Prospective collection of biological specimens other than blood: NONE

#### **Review of medical records, images, specimens – Category 5**

**For review of existing data:** provide a date range or an end date for when the data was generated. The end date can be the date this application was submitted to the IRB. Example: 01/01/1999 to 12/31/2015 or all records through mm/dd/yyyy.

**Date Range:** All records through 8/3/2018

Check all that apply (data includes medical records, images, specimens).

(5a) No data will be collected beyond the IRB submission date.

(5b) The study involves data that exist at the time of IRB submission **and** data that will be collected after IRB submission. Include this activity in the study design section.

Examples

- The study plans to conduct a retrospective chart review and ask subjects to complete a questionnaire.
- The study plans to include subjects previously diagnosed with a specific disease and add newly diagnosed subjects in the future.

(5c) The study will use data that have been collected under another IRB protocol. Include in the Methods section and enter the IRB number from which the research material will be obtained. *When appropriate, note when subjects have provided consent for future use of their data and/or specimens as described in this protocol.*

Enter one IRB number per line, add more lines as needed

Data    Specimens    Data & Specimens \_\_\_\_\_

Data    Specimens    Data & Specimens \_\_\_\_\_

Data    Specimens    Data & Specimens \_\_\_\_\_

(5d) This study will obtain data generated from other sources. Examples may include receiving data from participating sites or an external collaborator, accessing an external database or registry, etc. Explain the source and how the data will be used in the Methods section.

(6) Video audio recording: *Describe the plan to maintain subject privacy and data confidentiality, transcription, store or destroy, etc.*

#### **HIPAA Identifiers and Protected Health Information (PHI)**

Protected health information is medical data that can be linked to the subject directly or through a combination of indirect identifiers.

Recording identifiers (including a code) during the conduct of the study allows you to return to the medical record or data source to delete duplicate subjects, check a missing or questionable entry, add new data points, etc. De-identified data is medical information that has been stripped of all HIPAA identifiers so that it cannot be linked back to the subject. De-identified data is **rarely** used in the conduct of a research study involving a chart review.

**Review the list of subject identifiers below and, if applicable, check the box next to each HIPAA identifier being recorded at the time of data collection or abstraction.** Identifiers apply to any subject enrolled in the study including Mayo Clinic staff, patients and their relatives and household members.

**Internal** refers to the subject's identifier that will be recorded at Mayo Clinic by the study staff.

**External** refers to the subject's identifier that will be shared outside of Mayo Clinic.

| Check all that apply:   | INTERNAL                      | EXTERNAL                                 |
|--|-------------------------------|--|
| Name   | X                             |  |
| Mayo Clinic medical record or patient registration number, lab accession, specimen or radiologic image number  | X                             |  |
| Subject ID, subject code or any other person-specific unique identifying number, characteristic or code that can link the subject to their medical data  |                               |  |
| Dates: All elements of dates [month, day, and year] directly related to an individual, their birth date, date of death, date of diagnosis, etc.
Note: Recording a year only is not a unique identifier. | X                             |  |
| Social Security number   |                               |  |
| Medical device identifiers and serial numbers  | X                             |  |
| Biometric identifiers, including finger and voice prints, full face photographic images and any comparable images  |                               |  |
| Web Universal Resource Locators (URLs), Internet Protocol (IP) address numbers, email address  |                               |  |
| Street address, city, county, precinct, zip code, and their equivalent geocodes  | X                             |  |
| Phone or fax numbers   | X                             |  |
| Account, member, certificate or professional license numbers, health beneficiary numbers   |                               |  |
| Vehicle identifiers and serial numbers, including license plate numbers  |                               |  |
| Check 'None' when none of the identifiers listed above will be recorded, maintained, or shared during the conduct of this study. (exempt category 4)  |  None |  None |

